7.4. Interim Analysis Plan

[figure not shown]
Interim Analysis for Efficacy and Safety

This two-sided symmetrical group sequential design, which is based upon the existing sample size specified in the protocol (N=77), has two planned stages: 1 interim stage at information fraction 0.67 (n=52) and a final stage (N=77). We will implement the two-sided O'Brien-Fleming methodology to monitor the clinical trial for early stopping because of efficacy or "safety" (exacerbated anxiety). The latter is not anticipated, but will be evaluated. We used the procedures of PROC SEQDESIGN in SAS to create the group sequential design by computing boundary values for the stages (based on the O'Brien-Fleming methodology). The boundary values are derived in such a way that the overall Type I (0.05) and Type II (0.20) error probability levels will be maintained in this design. With early stopping to reject the null hypothesis, the lower rejection boundary is constructed by connecting the lower critical values (on the Z scale) for the stages. Similarly, the upper rejection boundary is constructed by connecting the upper critical values (on the Z scale) for the stages. See Table 1 and Figure 1 (boundary plot).

We will then use the procedures of PROC SEQTEST in SAS to compare the obtained test statistic with these boundary values (at each stage) to evaluate the trial for stopping. For this two-sided symmetrical group sequential design, a standardized Z test statistic will be computed by standardizing the estimate of the effect in Preoperative Anxiety, and a negative Z test statistic indicates a beneficial effect. Thus, at the interim stage, if the standardized Z test statistic is less than or equal to the corresponding lower alpha boundary value, the null hypothesis is rejected for efficacy and the trial will be considered for stopping. Conversely, while not anticipated, if the standardized Z test statistic is greater than or equal to the corresponding upper alpha boundary value, the null hypothesis is rejected for a "harmful/safety" effect (exacerbated anxiety) and the trial will be considered for stopping. Otherwise, the process continues to the next stage. At the final stage (stage 2), the null hypothesis is rejected for efficacy if the Z statistic is less than or equal to the corresponding lower alpha boundary value of -2.004, and the null hypothesis is rejected for a "harmful/safety" effect if the Z statistic is greater than or equal to the corresponding upper alpha boundary value of 2.004. Otherwise, the null hypothesis is not rejected. When the trial is stopped at either the interim stage or at the final stage, the SEQTEST procedure can also be used to derive parameter estimates, confidence limits for the parameter, and p-values for hypothesis testing.

Figure 1.

Boundary Plot, which corresponds to the information in Table 1.

Note. Fixed Sample Design Critical Values ($\alpha=0.05$ two-sided): ± 1.96 .Note. Two planned stages: 1 interim stage at information fraction 0.67 ($n=52$) and a final stage ($N=77$).**Table 1.**Nominal Critical Values and Alpha Levels for a two-sided symmetrical group sequential design, with 2 stages, for Efficacy and Safety (O'Brien-Fleming, $\alpha=0.05$ two-sided, $\beta=0.20$)

Stage	Sample Size (N)	Nominal Critical Value (Z-value scale)	Nominal Alpha Level Lower	Nominal Alpha Level Upper	Nominal Alpha Level (two-sided)
1	52	± 2.431	0.00737	0.00737	0.01474
Final	77	± 2.004	0.02280	0.02280	0.04560

Note. Fixed Sample Design Critical Values ($\alpha=0.05$ two-sided): ± 1.96 .**Interim Analysis for Futility**

Futility analyses are planned to be conducted to coincide in timing with the tentatively scheduled interim analysis for efficacy and "safety" at each stage of

information. The stochastic curtailment method is adopted based on conditional power (Lan et al, 1982). The informal criterion for determination of futility is that at the interim stage, if the conditional power (defined as the probability of rejecting the null hypothesis of no effect once some data are available at each stage) is low (e.g., <20%), then a conclusion could be reached that it would be futile to continue the trial. At this juncture, the research team will evaluate all study information to consider stopping the study for futility. The evaluation will be conducted in a blinded manner.

Evaluation of futility using conditional power allows flexibility in that it can be calculated and assessed at any time during the study without inflation of the Type I error probability and that the threshold does not necessarily have to be pre-specified. This approach to assessing futility holds appeal because it allows other information to be taken into consideration such as recruitment and safety data and conditional power at other alternative effect sizes (Freidlin B and Korn EL, 2002). We will use the procedures of PROC SEQTEST in SAS to compute conditional power at each stage of the group sequential trial.

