7.3 Data Analyses

Categorical outcomes will be presented as frequency and percentages and compared using chi-square and/or Fisher's exact test. Continuous outcomes will be summarized by median and inter-quartile range (IQR) OR mean and standard deviation (depending on the data's distribution). Depending on the data's distribution a paired t-test or Wilcoxon-sign rank test will be performed to assess the difference between VR distraction and Non-VR distraction. For this crossover design a mixed model will also be implemented, which accounts for

treatment/intervention (VR vs. non-VR), sequence, and period as fixed effects. Patients will be nested within sequence.

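### Read plainly, section 7.4 gives an overall type I error of about 0.056, not 0.05, for the paired-t or mixed-model analysis, because an estimated-SD ratio is held to normal boundaries

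*Combined protocol and SAP*

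**What the plan says.** Section 7.4 sets up a two-stage, two-sided symmetric O'Brien-Fleming design with looks at 52 and 77 patients, and claims that "the overall Type I (0.05) and Type II (0.20) error probability levels will be maintained in this design". Table 1 gives critical values on the Z scale of ±2.431 and ±2.004. For the comparison, "a standardized Z test statistic will be computed by standardizing the estimate of the effect in Preoperative Anxiety"; the null hypothesis is rejected when that value reaches a boundary.

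Section 7.3 analyses the same crossover data differently: depending on distribution, "a paired t-test or Wilcoxon-sign rank test will be performed to assess the difference" between the two distraction methods, and a mixed model with treatment, sequence and period is also fitted. Section 7.2 gives a difference of 3.5 and an assumed SD of 10.

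Neither 7.3 nor 7.4 says where the standard error of the Z statistic comes from, names a t reference for the boundary comparison, or describes a conversion from p-value to Z.

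**The concern.** The boundaries are derived for a statistic that is exactly standard normal under the null. Here the SD is not known, so the estimate divided by its standard error has heavier tails: t with 51 degrees of freedom at the interim and 76 at the end, fewer with attrition. Normal cut-offs then reject too often, in the efficacy and the harm direction alike.

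At stake is a property that the plan states outright, overall error of 0.05. The relative effect is largest at the interim look, where early stopping is considered.

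**Working it through.** **Inputs.** Looks at 52 and 77, boundaries 2.431 and 2.004, alpha 0.05 (section 7.4, Table 1). Difference 3.5, SD 10, 10% attrition (section 7.2). I take SD 10 as the SD of the paired difference, which the plan does not say; this matters only for the power figures. Futility is treated as non-binding because 7.4 calls its criterion informal.

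**1. The plan's own figure.** With known variance, the two Z statistics have correlation √(52/77) = √0.675 = 0.822. O'Brien-Fleming sets b1 = b2/√t = 2.004/0.822 = 2.44 (2.439 unrounded). The probability of crossing at either look is 0.0500 with 2.439/2.004 and 0.0502 with the printed 2.431/2.004. The 0.05 is therefore reproduced for a true Z.

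**2. Tails at each look with an estimated SD.** The statistic is T = mean difference / (s/√n), with s taken from the data at that look.

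| Look | Cut-off | Normal tail (two-sided) | t tail (two-sided) |
|---|---|---|---|
| Interim, 51 df | 2.431 | 0.0151 | 0.0186 |
| Final, 76 df | 2.004 | 0.0451 | 0.0486 |

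**3. Overall error.** Null trials with normal paired differences were simulated (16 to 20 million per case, Monte Carlo SE about 0.00005), with s re-estimated at each look. A trial rejects if |T1| ≥ b1 or |T2| ≥ b2.

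| Case | Overall two-sided error |
|---|---|
| 52/77 pairs, printed 2.431/2.004 | 0.0557 |
| 52/77, one further df lost (crossover model) | 0.0557 |
| 52/77, 2.439/2.004 | 0.0555 |
| 47/69 pairs (52 × 0.9 = 46.8; 77 × 0.9 = 69.3), printed boundaries | 0.0562 |
| 52/77, Wilcoxon with normal approximation, printed boundaries (400,000 trials) | 0.0498 |

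**4. Where the excess comes from.** 0.0557 − 0.0500 = 0.0057. About 0.0002 of this is the printed 2.431 in place of 2.439 (step 1). A single look with a paired t at n=77 against 1.96 would already give 0.0535, so 0.0035 of the 0.0057 is the ordinary normal approximation.

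**5. After conversion.** Take the two-sided p-value p from the t reference and set Z = sign(T) × Φ⁻¹(1 − p/2). Against the printed boundaries this is the same as t cut-offs of 2.516 (51 df) and 2.038 (76 df). The overall error is 0.0505, and also about 0.0505 with 47/69 pairs.

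**6. Power at 3.5/10 = 0.35 SD.** Before and after conversion: 0.861 and 0.853 with 77 pairs; about 0.82 and 0.81 with 69.

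**7. Table 1.** 2 × (1 − Φ(2.431)) = 0.01506, but the printed alpha is 0.01474 (which belongs to 2.439). 2 × (1 − Φ(2.004)) = 0.04507, but the printed alpha is 0.04560 (which belongs to 1.999).

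**The case against.** The plan never says that an unconverted t ratio will be used. A t p-value turned into a normal deviate is also a standardized Z, and a programmer who did this without being told would get about 0.0505. That stands: a reader might infer that the trial's true error is 0.056 without qualification, and the documents support this only on the plain reading of 7.4.

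Two further limits stand. Section 7.3 leaves the test to the data's distribution, and the Wilcoxon branch shows no inflation. And if the futility guide (conditional power below 20%) were always enforced, the error would be 0.049 to 0.050 under the current trend or 0.037 under the design effect. But 7.4 keeps futility informal, so it cannot be counted on to control type I error.

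A reader might also infer that 7.3 and 7.4 give contradictory decisions on the same data. Take t = 2.01 on 68 df, p = 0.0484. It exceeds 2.004, so 7.4 rejects, but an ordinary paired t-test at 0.05 rejects too. They disagree only if the 7.3 p-value is held to the final nominal level (0.0451, or the printed 0.0456), and 7.3 sets no such threshold. The documents do not establish a conflict.

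Finally, normal-scale boundaries are common large-sample practice, the study is a pilot, and crossing at the interim leads only to stopping being considered. These points lower the severity. They do not restore the stated 0.05.

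**Conclusion.** The point holds in a limited form. If the effect estimate is divided by its estimated standard error and compared directly with 2.431 and 2.004, the overall two-sided type I error is about 0.056 for the paired-t or mixed-model analysis. The excess over the stated 0.05 is about 0.006.

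This assumes normal paired differences, no conversion from t to Z, and non-binding futility. It is separate from the Table 1 mismatch, since the error is still about 0.0555 with 2.439. Severity is low: the stated rule misses a stated property by a small margin, and one sentence corrects it.

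**What to change.** State in 7.4 that, at each look, the two-sided p-value from the 7.3 analysis used for the decision (t reference with its degrees of freedom) is converted to an equivalent Z, keeping the sign of the effect, before it is compared with the Z boundaries in SEQTEST. Section 7.3 offers several analyses, so the sentence must name the deciding one. Overall error is then about 0.050 to 0.051.

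If p-values are compared with nominal alphas instead, correct Table 1 first; otherwise the outcome depends on which column is used.

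The cost is one sentence, one line of code and about one point of power (step 6), which stays above the planned 0.80. Sample size and interim timing do not change, and under the conversion route neither do the boundaries.

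### Table 1: the Z critical values and nominal alphas disagree at both stages, and no single information fraction reproduces the table

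*Combined protocol and SAP*

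**What the plan says.** Section 7.4 describes a symmetrical two-sided O'Brien-Fleming design with an overall type I error of 0.05. There is one interim look, at information fraction 0.67 (n=52), and a final analysis at N=77. The boundaries are attributed to SAS: "We used the procedures of PROC SEQDESIGN in SAS to create the group sequential design by computing boundary values for the stages".

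Table 1 lists, for each stage, a critical Z, the lower and upper nominal alphas and the two-sided alpha:

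- Stage 1 (n=52): ± "2.431 0.00737 0.00737 0.01474"
- Final (N=77): ± "2.004 0.02280 0.02280 0.04560"

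The decision rules are written on the Z scale. At the final stage the number appears in the text: the null hypothesis is rejected for efficacy if Z is "less than or equal to the corresponding lower alpha boundary value of -2.004", with the mirror-image rule for harm. At the interim the text gives no number: "if the standardized Z test statistic is less than or equal to the corresponding lower alpha boundary value, the null hypothesis is rejected for efficacy". The consequence of crossing there is that "the null hypothesis is rejected for efficacy and the trial will be considered for stopping". The comparison is to be made in software: "We will then use the procedures of PROC SEQTEST in SAS to compare the obtained test statistic with these boundary values (at each stage"). Figure 1 is captioned "Boundary Plot, which corresponds to the information in Table 1", but the figure is not reproduced in the text available.

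**The concern.** A nominal alpha is simply the normal tail area beyond the critical Z, so the columns of Table 1 are two expressions of one boundary and must agree. They do not agree in either row.

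Two columns that disagree give two answers near the boundary. An interim two-sided p of 0.0148 to 0.0150 crosses by the Z column but not by the alpha column. A final two-sided p of 0.0452 to 0.0455 is significant by the alpha column but not by the Z column. The interim boundary also serves both the efficacy rule and the rule for worsened anxiety, and the supplied text gives its numerical value only in Table 1. If the printed interim Z is wrong, a reader has nothing else in the text from which to recover the right one.

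**Working it through.** **Inputs (Section 7.4).** Overall two-sided alpha 0.05; O'Brien-Fleming boundaries; information fraction t stated as 0.67, with sample sizes giving 52/77 = 0.6753; Table 1 as printed.

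**Step 1: do the columns agree?** Alpha per side = 1 − Φ(Z).

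| Stage | Printed Z | Alpha implied, per side (two-sided) | Alpha printed, per side (two-sided) | Z implied by printed alpha |
|---|---|---|---|---|
| 1 | 2.431 | 0.00753 (0.01506) | 0.00737 (0.01474) | 2.4387 |
| Final | 2.004 | 0.02254 (0.04507) | 0.02280 (0.04560) | 1.9991 |

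The printed alphas are consistent among themselves: 2 × 0.00737 = 0.01474 and 2 × 0.02280 = 0.04560.

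Rounding of Z does not close either gap. Any Z from 2.4305 to 2.4315 gives 0.00754 down to 0.00752. Any Z from 2.0035 to 2.0045 gives 0.02256 down to 0.02251. Tails of the t-distribution (50, 51, 75 or 76 degrees of freedom) do not help: 2.431 gives about 0.0087 to 0.0093, and 2.004 about 0.0243 to 0.0253.

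**Step 2: what does the stated design give?** For two-stage O'Brien-Fleming, the final boundary is C and the interim boundary is C/√t. C solves

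1 − P(|Z₁| < C/√t, |Z₂| < C) = 0.05, with corr(Z₁, Z₂) = √t.

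| t | Interim Z (per side) | Final Z (per side) | Printed figures matched |
|---|---|---|---|
| 0.67 exactly | 2.447 (0.00719) | 2.003 (0.02257) | none |
| 52/77 | 2.439 (0.00737) | 2.004 (0.02253) | interim alpha, final Z |
| 0.68 | 2.431 (0.00752) | 2.005 (0.02249) | interim Z |

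**Step 3: which t would print each figure?** Solving the same equation for t, with each figure's rounding limits:

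- Interim Z 2.431: t from 0.6799 to 0.6805
- Interim alpha 0.00737: t from 0.6752 to 0.6755
- Final Z 2.004: t from 0.6712 to 0.6775
- Final alpha 0.02280: t from 0.6429 to 0.6440

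Only the second and third ranges overlap, and 52/77 lies in that overlap. The two entries of the Z column do not share a value of t either. O'Brien-Fleming-type Lan-DeMets spending, applied two-sided or per side and scanned over t from 0.62 to 0.72, matches at most one figure at any t.

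**Step 4: what does it cost in type I error?** Overall two-sided alpha if the printed values are applied:

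| t | Z column (2.431, 2.004) | Alpha column (2.4387, 1.9991) |
|---|---|---|
| 52/77 | 0.0502 | 0.0505 |
| 0.67 | 0.0503 | 0.0506 |
| 0.68 | 0.0501 | 0.0504 |

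Under the null hypothesis, the probability that the interim |Z| falls between 2.431 and the O'Brien-Fleming boundary is 2 × (0.007529 − 0.007368) = 0.0003 at 52/77, and 2 × (0.007529 − 0.007194) = 0.0007 at 0.67.

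**The case against.** **Only Z decides.** Every stated rule is on the Z scale, and no rule applies the nominal alphas. The final rule of ±2.004 is right at 52/77. This stands: the final-row error is descriptive, and the final-stage conflict arises only for someone who reads significance from the alpha column. It does not rescue the interim Z, which feeds a rule and is too lenient at both stated fractions (2.431 against 2.439 or 2.447).

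**A digit may have been misread.** The text was machine-read, 2.431 appears once, and 2.439 differs from it in one digit. This cannot be excluded without the source table, but nothing points to it, and the final-row alphas would still be wrong.

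**0.67 is a rounded figure.** Read as 0.665 to 0.675 it overlaps the range for the final Z, and read as a truncation of 0.6753 it fits two figures. That is fair, and it is why the tables above treat 0.67 and 52/77 separately. It leaves the mismatch within each row untouched.

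**52/77 may not be the realised fraction.** Section 7.2 allows for 10% attrition within the 77, and the plan does not say whether 52 and 77 count enrolled patients or completers. If 52 were completers and 77 × 0.9 ≈ 69 finished, the fraction would be 52/69 ≈ 0.75. The replacement values therefore reproduce the nominal design, and the fraction must be declared by the sponsor.

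**The effect is negligible.** SEQTEST may use boundaries held in the SEQDESIGN output, and crossing leads only to considering a stop. Both points are accepted and set the rating.

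**Conclusion.** The concern holds, as a minor error. That the printed Z values and alphas disagree in both rows is a matter of normal tail areas and depends on no assumption about the boundary family or the information fraction. It follows that no fraction can reproduce the whole table.

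Which cells are wrong is an inference, since the SEQDESIGN output and Figure 1 are not available. On the stated O'Brien-Fleming design at 52/77, the interim Z and the final-stage alphas are the likely errors. A fraction of 0.68, which is 52/77 rounded but appears nowhere in the plan, would explain the interim Z and nothing else.

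The overall alpha exceeds the stated 0.05 by at most 0.0003 with the printed Z column and 0.0006 with the printed alpha column, across the three fractions examined. The interim Z matters in practice only if the printed number is applied in place of the software's stored boundary.

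**What to change.** Declare one information fraction, say whether it counts enrolled patients or completers, and regenerate Table 1 from it. If 52/77 is meant, the rows become:

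| Stage | Z | Lower | Upper | Two-sided |
|---|---|---|---|---|
| 1 | ±2.439 | 0.00737 | 0.00737 | 0.01474 |
| Final | ±2.004 | 0.02253 | 0.02253 | 0.04505 |

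State the interim Z in the text, as is already done for the final stage, and add that the Z scale governs and the alphas are descriptive. Check Figure 1 and the SEQDESIGN output against the corrected values.

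The cost is a table correction and a sentence or two. At 52/77 the interim threshold becomes marginally stricter (2.431 to 2.439), and the final rule, sample size and patient procedures do not change.

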8.0 STUDY MANAGEMENT

8.1 Conflict of Interest

Any investigator who has a conflict of interest with this study (patent ownership, royalties, or financial gain greater than the minimum allowable by their institution, etc.) must have the conflict reviewed by the UTSW COI Committee and IRB according to UTSW Policy on Conflicts of Interest. All investigators will follow the University conflict of interest policy.

8.2 Institutional Review Board (IRB) Approval and Consent

It is expected that the IRB will have the proper representation and function in accordance with federally mandated regulations. The IRB must approve the consent form and protocol.

In obtaining verbal or written informed consent and documentation, the investigator should comply with the applicable regulatory requirement(s) and should adhere to Good Clinical Practice (GCP) and to ethical principles that have their origin in the Declaration of Helsinki.

Potential subjects will be identified from the CCBD schedule. Subjects are not patients of the study investigator, so a member of the study staff will request permission from the treating team to approach and include subjects in the study. The legal authorization of parents to be approached will be verified by a member of the study team before approaching them. The study will be explained to the subject (if old enough to participate in discussion) and the parents the night before their CCBD visit by a named member of the study team designated to perform the task of obtaining informed consent. It will be explained that participation is completely voluntary and that whether they choose to participate or not will not affect their treatment in our facility. They will be given ample time to consider participation and ask any questions they may have with the study team members and their treating physician.

Once verbal consent from the LARs and verbal assent from study participant (if old enough to participate in the discussion) is obtained over the phone the night prior to the CCBD visit (see study schema), the researcher will prepare for the following day's mYPAS observation.

On the next day's CCBD visit, when the patient is placed in their CCBD holding room prior to port access, it will be verified that they are still interested in participating. If the LAR or patient has any additional questions, the researcher will be in the room virtually on the CHST telemedicine tablet platform to answer any further questions. Then, written informed consent will be obtained and a copy of the signed consent form will be given to the subject's LAR by their nurse or the child life specialist.

Children's Medical Center has a large Hispanic population; therefore, the study will be discussed using a certified on-site Spanish translator, if a language barrier exists. Fully translated Spanish versions of the parent questionnaires and the study consent form will be provided.

The study PI will keep a list of study subjects on a firewalled Children's Medical Center (Dallas Campus) computer which links study number with the study subject. This study subject list will be kept in a password protected file accessible only to the faculty mentor and the PI for the duration of the study. To protect PHI, this list will be deleted at the end of the study.

Randomized Pilot Crossover Study Comparing Virtual Reality (VR) and Non-VR Distraction for Decreasing Preoperative/Procedural Anxiety as a Function of the modified Yale Preoperative Anxiety Scale (mYPAS)

